6 ESTIMAND

6.1 Estimand for the Primary Objective

The primary estimand is defined through the following estimand attributes:

6.1.1 Treatment and Target Population

The target population of the estimand for the primary objective is all subjects who have at least one evaluable HM15912 serum concentration after receiving any amount of HM15912 without IPDs or events that significantly affect the PK of HM15912. This population is represented in this trial by PK Population.

6.1.2 Intercurrent Event and Handling Strategies

Table 4 Handling of Intercurrent Events for the Primary Estimand

| Intercurrent event | Data collection and analysis |
|---------------------------------|---|
| Use of prohibited medication | Depending on the assessment of the type of prohibited medication in the determination of PK Population, data collected after the intercurrent event will be used in analysis in line with a treatment policy strategy or a while on-treatment policy. |
| Early withdrawal from the study | Depending on the assessment of the timing of early withdrawal from the study in the determination of PK Population, the intercurrent event will be handled via a while on-treatment policy. |

6.1.3 Variable and Population-level Summary

To evaluate the effect of severe renal impairment on the pharmacokinetics of HM15912

following single SC dose, PK parameters will be summarized by endpoint as presented in Table 5.

Table 5 Population level summary for Primary endpoints

| Primary endpoint | Population-level summary |
|--|--|
| Maximum serum concentration (C_{max}) | |
| Area under the concentration-time curve from extrapolated to infinity ($AUC_{0-\infty}$) | Geometric mean ratio (GMR) and corresponding 90% confidence interval (90% CI) between each renal impairment cohort and normal renal function cohort (i.e. Cohort 2, Cohort 3, Cohort 4 versus Cohort 1, respectively) will be presented with descriptive statistics [number of subjects, arithmetic mean, SD, coefficient of variation (CV%), geometric mean, geometric mean CV% median, minimum, and maximum values]. |

To explore the robustness of inferences from the main estimator, a sensitivity analysis will be conducted targeting the same estimand. If the adjusted regression coefficient (R^2) is less than 0.8 or the extrapolated area under the curve ($AUC_{\%Extrap}$) exceeds 20%, those will be excluded from the sensitivity analysis.

6.2 Estimand for the Secondary Objective

The secondary estimand is defined through the following estimand attributes:

6.2.1 Treatment and Target Population

The target population of the estimand for the secondary objective is all subjects who received any amount of HM15912. This population is represented in this trial by Safety Population.

6.2.2 Intercurrent Event and Handling Strategies

Table 6 Handling of Intercurrent Events for the Secondary Estimand

| Intercurrent event | Data collection and analysis |
|------------------------------|---|
| Use of prohibited medication | Intercurrent events will be handled via a while on-treatment policy with a residual treatment effect period strategy. All intercurrent events will be ignored because of residual treatment effect. Safety summaries will be based on the available safety data collected until the last study visit. |

6.2.3 Variable and Population-level Summary

To evaluate the safety and tolerability of a single SC dose of HM15912 in subjects between mild, moderate and severe renal impairment and normal renal function subjects, secondary

endpoints will be summarized as presented in Table 7.

Table 7 Population level summary for Secondary endpoints

| Secondary endpoint | Population-level summary |
|--|---|
| Incidence of AEs, TEAEs, and SAEs | Number and percentages of subjects with TEAEs and SAE by cohort and in total. AEs which are occurred after signing of ICF and before first study drug administration will be included in by-subject listing with TEAE flag, and will not be summarized. |
| Change from baseline in vital signs and 12-lead ECG parameters | Descriptive statistics of change from baseline in vital signs and 12-lead ECG parameters by cohort and in total. |

7 GENERAL STATISTICAL CONSIDERATION

All statistical analyses will follow the rules which is planned in this section unless other specified.

7.1 Summary and Representation of Data

In general, data will be summarized with descriptive statistics (number of subjects, mean, standard deviation (SD), median, minimum, and maximum) for continuous variables, and number of subjects and percentages for categorical variables. All summaries and analyses will be presented by cohort and in total where applicable. By visit or timepoint analysis results will be summarized appropriately using nominal visit or timepoint as defined in the Schedule of Assessments.

For summary statistics, the arithmetic mean and median will be displayed to one more decimal place than the raw data and SD will be displayed to two more decimal places than the raw data. The minimum and maximum will be displayed to the same number of decimal places as the raw data. Percentages will be presented to one decimal place, and will not be presented for zero counts. The denominator in percentage calculations will be the number of subjects in each treatment group within the relevant analysis set. In general, the maximum number of decimal places reported shall be four for any summary statistic.

For pharmacokinetic analysis, data will be summarized with N (number of subjects), n (number of subjects with non-missing values), and n(BLQ) (number of subjects with BLQ samples), arithmetic mean, SD, coefficient of variation (CV%), geometric mean, geometric mean CV% (calculated as: $gCV\% = \text{SQRT}(e^{s^2}-1)*100$; where s is the SD of the log-transformed values), median, minimum, and maximum values, except for t_{max} and $t_{1/2}$.

Point estimate of geometric mean ratio and corresponding confidence interval (CI) will be presented to two decimal places.

All recorded and derived data which are related with analysis of this SAP will be presented in

the by-subject listing for Screened population. Each subject's cohort information and defined analysis population will be presented for all listings.

7.2 Baseline

The baseline value is defined as the last non-missing measurements collected prior to the first study drug administration. Repeat and unscheduled assessments will be included in the derivation of the baseline values. Change from baseline and percent change from baseline will be calculated as below only when the both baseline and post-baseline values are available in each subjects.

- Change from Baseline = Post-baseline – Baseline
- Percent Change from Baseline (%) = $(\text{Post-baseline} - \text{Baseline}) / \text{Baseline} * 100$

7.3 Repeat and Unscheduled Data

Values collected at scheduled study visits/time points will be presented in summary tables. If a repeat assessment was performed, the result from the original assessment will be presented as the result at the specific visit and time point. All collected data will be included in the data listings.

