7.4. Lost to Follow up

A subject will be considered lost to follow-up if he or she repeatedly fails to return for scheduled visits and is unable to be contacted by the study site.

The following actions must be taken if a subject fails to return to the clinic for a required study visit:

- The site must attempt to contact the subject and reschedule the missed visit as soon as possible and counsel the subject on the importance of maintaining the assigned visit schedule and ascertain whether or not the subject wishes to and/or should continue in the study.
- Before a subject is deemed lost to follow up, the investigator or designee must make every effort to regain contact with the subject (where possible, 3 telephone calls and, if necessary, a certified letter to the subject's last known mailing address or local equivalent methods). These contact attempts should be documented in the subject's medical record.
- Should the subject continue to be unreachable, he/she will be considered to have withdrawn from the study.

Discontinuation of specific sites or of the study as a whole are handled as part of Appendix 1.

8. Study Assessments and Procedures

- Study procedures and their timing are summarized in the SoA (Section 1.2). Protocol waivers or exemptions are not allowed.
- Immediate safety concerns should be discussed with medical monitor or the sponsor immediately upon occurrence or awareness to determine if the subject should continue or discontinue study intervention.
- Adherence to the study design requirements, including those specified in the SoA (Section 1.2), is essential and required for study conduct.
- All screening evaluations must be completed and reviewed to confirm that potential subjects meet all eligibility criteria. The investigator will maintain a screening log to record details of all subjects screened and to confirm eligibility or record reasons for screening failure, as applicable.
- Procedures conducted as part of the subject's routine clinical management (e.g., blood count) and obtained before signing of the ICF may be utilized for screening or baseline purposes provided the procedures met the protocol-specified criteria and were performed within the time frame defined in the SoA (Section 1.2).
- The maximum amount of blood collected from each subject over the duration of the study will be in line with local regulations. Repeat or unscheduled samples may be taken for safety reasons or for technical issues with the samples.

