8.2.3. Electrocardiograms

- A 12 lead ECG will be obtained at scheduled timepoints in the SoA (Section 1.2) using an ECG machine that automatically calculates the HR and measures PR, QRS, QT, and QTc intervals. Additional ECGs will be performed for cause as needed to evaluate AEs.
- The 12-lead ECGs will be performed after the subject has been resting supine for ≥ 5 minutes.
- A triplicate 12-lead ECGs will be performed at screening period and Day1. At all other times, however, single 12-lead ECGs will be performed as outlined in the SoA (Section 1.2).
- Limited to Day 1, ECGs will be performed at predose and at 4 hours postdose, and a ± 30 -minute assessment window is allowed for measurement 4 hours postdose.
- The triplicate ECGs will be recorded at least 30 seconds apart from each other, not exceeding a time period of 3 minutes for the completion of all 3 ECGs.
- Investigator's assessment of clinical significance ('abnormal, not clinically significant' or 'abnormal, clinically significant') will be recorded in the eCRF. Centralized ECG vendor will be used for ECG measurement and independent reading.

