9.3.2 Clinical Laboratory Assessments

Clinical laboratory test results performed by the central laboratory will be summarized for the parameters below:

Table 9 Clinical Laboratory Parameters

| Hematology | Coagulation | Clinical Chemistry | Urinalysis |
|--|--|---|---|
| 
 • RBC count • WBC count (with differential) • Neutrophils • Eosinophils • Basophils • Lymphocytes • Monocytes • Platelet count • Hemoglobin • Hematocrit • RBC indices: MCV • MCH • %Reticulocytes | 
 • PT (INR) • aPTT | 
 • Fasting plasma glucose • BUN • Creatinine • Potassium • Sodium • AST • ALT • GGT • Alkaline phosphatase • Total and direct bilirubin | 
 • Specific gravity • pH, glucose, protein, blood, ketones, bilirubin, urobilinogen, nitrite, leukocyte esterase by dipstick • Microscopic examination (if blood or protein is abnormal) • Pregnancy test |

Abbreviations: ALT = alanine aminotransferase; aPTT = activated partial thromboplastin time; AST = aspartate aminotransferase; BUN = blood urea nitrogen; GGT = gamma-glutamyl transferase; INR = international normalized ratio; MCH = mean corpuscular hemoglobin; MCV = mean corpuscular volume; PT = prothrombin time; RBC = red blood cell; WBC = white blood cell.

By nominal visit and timepoint, observed value and the change from baseline value of quantitative laboratory parameters will be summarized using descriptive statistics, and the frequency tabulation for the qualitative laboratory parameters will also be provided.

Any quantitative laboratory parameters that are given as '<xx' or '>xx' in the database will be replaced with the value without the sign (e.g., <2.2 will be imputed as 2.2) for the summarization purpose.

Each laboratory test results will be evaluated by the investigator as 'Normal', 'Abnormal, Not Clinically Significant', or 'Abnormal, Clinically Significant'. Shift tables will be generated showing the number and percentage of subjects with shifts from baseline to each post-baseline visit.

All by-visit summary of laboratory test data will be provided based on the test results at scheduled visit, but all the data will be listed by subject regardless of measurements at scheduled or unscheduled.

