9.3.4 Physical Examination

Physical examination findings ('Normal', 'Abnormal, Not Clinically Significant', and 'Abnormal, Clinically Significant'), height, weight, and BMI will be listed by subject.

9.3.5 12-lead Electrocardiograms

A triplicate 12-lead ECGs will be performed at screening period and Day 1. At all other times, however, single 12-lead ECGs will be performed. For the ECGs measurement taken in triplicate, mean of the triplicates measurements will be used as baseline and post-baseline

value of each visit and timepoint. If there is missing data among the triplicated measurements, only the non-missing value will be used to calculate the mean value.

Automatically calculated HR, PR, QRS, QT, and corrected QT using the Fridericia correction formula (QTcF) will be used to summarize the observed value and change from baseline value by visit and timepoint.

Additional categorical analysis for the QT and QTcF will also be performed based on categories as below:

- Observed value: ≤450 ms, >450 and ≤480 ms, >480 and ≤500 ms, >500ms
- Change from baseline value: ≤30 ms, >30 ms and ≤60 ms, >60 ms

Overall interpretation ('Normal', 'Abnormal, Not Clinically Significant', or 'Abnormal, Clinically Significant') of 12-lead ECG will be summarized using shift table to compare the investigator's evaluation between baseline and each post-baseline visit and timepoint.

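### SAP 7.3 keeps post-dose unscheduled and repeat values out of the lab and ECG shift tables and, by default, the QT/QTcF category counts, and no worst-post-baseline summary is defined

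*SAP*

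**What the plan says.** SAP Section 7 sets the defaults: "All statistical analyses will follow the rules which is planned in this section unless other specified". Within it, SAP 7.3 says "Values collected at scheduled study visits/time points will be presented in summary tables". For a repeated test, "the result from the original assessment will be presented as the result at the specific visit and time point". Everything else is covered by "All collected data will be included in the data listings". SAP 7.1 adds that by-visit results use the nominal visits of the Schedule of Assessments.

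The safety sections follow this default.

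- **Labs (SAP 9.3.2):** "All by-visit summary of laboratory test data will be provided based on the test results at scheduled visit", with unscheduled results listed. Shift tables of the investigator's rating run from baseline to each post-baseline visit.
- **ECG (SAP 9.3.5):** shift tables are by visit and timepoint. Then "Additional categorical analysis for the QT and QTcF will also be performed based on categories as below", with value bands up to >500 ms and change bands up to >60 ms. The section does not say whether a subject is classified at each visit or once by the highest value.
- **Baseline (SAP 7.2):** repeat and unscheduled values are admitted.

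The protocol expects off-schedule data. Protocol 8.2.3 says "Additional ECGs will be performed for cause as needed to evaluate AEs". Protocol 8.2.4 has clinically significant lab abnormalities repeated until they settle. The opening bullets of Protocol Section 8 say "Repeat or unscheduled samples may be taken for safety reasons or for technical issues with the samples".

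**The concern.** Category counts and shift tables are where a reader looks for extremes. If they draw on scheduled values alone, and no row takes each subject's worst post-dose value, a marked finding between visits leaves no trace in them. Change in vital signs and ECG parameters is one of the two secondary endpoints, and the tables are meant to be compared across cohorts of 8, where a single subject is visible.

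The renal-impairment cohorts may also enter with QTcF up to 480 ms, against 450 ms (men) or 470 ms (women) in the controls (Protocol 5.2.2 and 5.2.3). The upper QTcF bands are therefore a place where cohorts could differ.

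**Working it through.** The plan gives no figure for this point. The check is a reading of the rules, a count of scheduled time points, and one proportion.

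**1. Does any later section override SAP 7.3?**

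| Table | Basis stated | Exception for unscheduled or repeat values | Worst-post-baseline row |
|---|---|---|---|
| Lab shifts (9.3.2) | each post-baseline visit; by-visit lab summaries on scheduled visits | none | none |
| ECG shifts (9.3.5) | each visit and timepoint | none | none |
| QT/QTcF categories (9.3.5) | not stated | none | none |

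For the two shift tables, exclusion follows directly. For the QT/QTcF categories it follows from the Section 7 default, because 9.3.5 is silent. SAP 6.2.2 bases safety summaries on the available data up to the last visit, but it does so as handling of prohibited medication and does not mention unscheduled or repeat values. I do not read it as an exception.

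**2. When would an off-schedule value be the only one near peak exposure?**

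Mean t_max in the first-in-human study was 71.8 to 142.9 h (Protocol 2.2). Nominal hours are 24 × (Day − 1).

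- ECGs after dosing: 4 h, then Days 2 to 8 daily, 10, 15, 22 and 29, giving 4, 24, 48, 72, 96, 120, 144, 168, 216, 336, 504 and 672 h. That is 12 time points, three of them (72, 96 and 120 h) inside the t_max range.
- Labs after Day 1: Days 2, 8, 15, 22 and 29, giving 24, 168, 336, 504 and 672 h. None is inside the range.

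A lab drawn on Days 3 to 7 is unscheduled by definition. The protocol itself generates off-schedule labs: retesting 48 to 72 hours after suspected liver injury (8.3.7.2) and weekly liver tests after a confirmed trigger (Appendix 5).

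**3. Size of one omission**

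- Cohort of 8: 1/8 = 12.5 percentage points.
- Part 1 total of 16: 1/16 = 6.25 points.
- All four cohorts, 32: 1/32 = 3.1 points.

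Illustration with assumed values: a subject whose scheduled QTcF never exceeds 470 ms has a for-cause reading of 505 ms. The >500 ms row shows 0/8. A maximum-post-baseline row would show 1/8.

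**The case against.** The case against giving this much weight has substance.

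- **Other tables count many of these subjects.** Clinically significant abnormalities are recorded as AEs (Protocol 8.2). TEAEs are tabulated by maximum severity, and suspected liver injury is an AESI with its own incidence table (SAP 9.3.1). None of these is limited to scheduled visits. This stands, but it is partial. It depends on investigator judgement, and findings associated with underlying disease are exempt unless more severe than expected (Protocol 8.2.4 and Appendix 3). That exemption is likely to bite more in the renal-impairment cohorts than in controls chosen without relevant abnormalities.
- **Repeats often record recovery.** The abnormal result that prompts a repeat stays in the table, so that value is not lost. This stands. A worst value drops out only if it occurs at an unscheduled time or if the repeat is worse than the result it follows.
- **ECGs are taken daily from Day 2 to Day 8.** This stands and makes the ECG gap smaller than the lab gap.
- **All results are listed, the study is small, and no hypothesis is tested.** This stands and limits the consequence, although listings do not give counts by cohort.

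A reader might go further and infer that the worst safety values are missing from the tables. The documents show only that they may be. A reader might also infer that unscheduled values are barred altogether. SAP 7.2 admits them to baseline, SAP 7.3 does not use the word only, and 9.3.5 leaves the QT/QTcF classification open.

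Three further extensions lack support. Nothing shows that a technically invalid sample would yield a reported value that stays in the table. The early-discontinuation visit is tied to the Day 29 assessments and is not shown to be excluded. I found no specific provision for off-schedule vital signs.

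**Conclusion.** The point holds in a limited form. Under SAP 7.3, unaltered by 9.3.2 or 9.3.5, post-dose unscheduled and repeat values stay out of the lab and ECG shift tables and, by default, out of the QT/QTcF category counts. No worst-post-baseline summary picks them up. This is a stated rule that can undercount, so it is more than a missing detail. It is most relevant to labs on Days 3 to 7.

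Each affected subject is 12.5 percentage points in a cohort of 8. How many will be affected cannot be known from the documents and may be none. The conclusion assumes that the Section 7 default governs the QT/QTcF categories.

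**What to change.** Keep all by-visit tables on scheduled values. In SAP 9.3.2 and 9.3.5, with a cross-reference in 7.3, add:

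1. a worst-post-baseline row in the lab and ECG shift tables;
2. a maximum-post-baseline row in the QTcF value and change categories, stating that each subject is counted once by the highest value;
3. a sentence that these rows use all post-dose values, whether scheduled, unscheduled or repeat.

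The cost is SAP wording and a few table rows from data already collected. The drawback is that subjects tested more often have more chances to show an extreme, so the rows are not a like-for-like comparison if cohorts differ in unscheduled testing. A footnote can say so.

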7.4 Handling of Missing Data

Except as stated below, there will be no imputation of missing values, and all data will be included in the by-subject listings as it is.

7.4.1 Missing or Partial Dates

In general, missing or partial date will not be imputed except for classification of Treatment Emergent Adverse Event (TEAE) or Concomitant Medication (CM). If the start and/or stop date are partial, the dates will be compared as far as possible with the date of first study drug administration. However, if the missing or partial date interrupts classification, adverse events or medication will be treated as TEAE or CM.

7.4.2 Missing Assessment of Adverse Event

If the assessment of the severity or relationship to study drug is missing for the AEs, the event will be classified as 'Severe (or Grade 3)' or 'Related', respectively, for summary purposes.

7.5 Study Day

The study day of an event is defined as the relative day of the event starting with the date of the first study drug administration (reference date) as Day 1. The date preceding first study drug administration is designated as study day -1 (there will be no Day 0).

- If the date of event is before the study drug administration, then:

- Study Day = (Date of event - Date of first study drug administration)
- If the date of event is on or after the study drug administration, then:
Study Day = (Date of event - Date of first study drug administration) + 1

Study days will only be calculated for events with complete dates and will be undefined for the end date of ongoing events at the end of the study.

7.6 End of Study

A subject is considered to have completed the study if subject has completed all periods of the study including the last scheduled procedure shown in the Schedule of Assessments. The end of the study is defined as the date of the last visit of the last subject in the study or last scheduled procedure for the last subject in the trial globally.

